### 1.3 Rationale

A recent investigator-led trial that explored whether early-start therapy with deferiprone could delay the progression of iron accumulation without inducing toxicity yielded promising results. Recently diagnosed thalassemia patients aged approximately 12 months were randomized to either start receiving deferiprone at a low dose of 50 mg/kg/day or to wait until their serum ferritin levels reached the threshold of 1000 µg/L recommended by current guidelines. All the subjects who were not receiving chelation reached this threshold at about 6 months post-baseline, after receipt of about 10 transfusions; in comparison, for those on deferiprone, none had reached it by 6 months, only 10% had reached it by 9 months, and the remainder reached it only at 12 months, after 16 to 18 transfusions. Large group differences were seen for other indices of iron overload as well. With respect to safety, there were no unexpected, serious, or severe adverse events associated with deferiprone treatment.

The current trial has been designed to further evaluate the early use of deferiprone in young children with newly diagnosed transfusion-dependent thalassemia. The objectives are to determine whether such a regimen can postpone saturation of transferrin and thus the appearance of labile plasma iron (considered the main source of iron overload in endocrine glands and myocytes) while maintaining a good safety profile. Participants in this trial will have already started on a transfusion regimen designed to maintain a hemoglobin level > 9 g/dL, but will still have a serum ferritin well below 1000 µg/L, which is the current standard for starting iron chelation therapy.

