### 9.2 Determination of Sample Size and Study Power

The sample size for this study is 64 patients, randomized in a 1:1 ratio to the two arms. With this number of patients, there will be over 90% power to detect a statistically significant difference ( $\alpha = 0.05$ ) between the two treatment groups in the percentage of patients who have a serum ferritin level  $< 1000 \mu\text{g/L}$  at Month 12 if the deferiprone arm and the placebo arm have an expected incidence of 70% and 20%, respectively.

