## **5. Statistical Analysis**

A two-sided p-value of 0.05 will be used as the significance level for the determination of statistical significance in all statistical tests.

All statistical analyses of efficacy and safety data will be performed using SAS (version 9.4 or higher) on the Windows operating system.

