### **5.2.2 Secondary Efficacy Endpoints**

The secondary efficacy endpoints are:

- The percentage of patients whose serum ferritin level is still less than 1000  $\mu\text{g}/\text{L}$  at each visit
- The percentage of patients whose LPI value is still less than 0.6  $\mu\text{M}$  at each visit
- The percentage of patients whose TSAT value is still less than 60% at each visit
- Time to reach a serum ferritin level  $\geq 1000 \mu\text{g}/\text{L}$  (Note: a patient is to be withdrawn from the study only if the repeated serum ferritin level is  $\geq 1000 \mu\text{g}/\text{L}$ .)
- Time to reach an LPI value  $\geq 0.6 \mu\text{M}$
- Time to reach a TSAT value  $\geq 60\%$

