## 5.6 Analysis of Efficacy

The percentage of patients who have not reached levels of  $LPI \geq 0.6 \mu M$ ,  $TSAT \geq 60\%$ , or  $SF \geq 1000 \mu g/L$  will be compared between the two treatment groups at each monthly time point as well as at the end of study, using the Fisher's exact test. (Note: the repeated SF value will be used to determine this for those patients whose SF is  $\geq 1000 \mu g/L$ .)

The effect of baseline value on each of the 3 efficacy endpoints will be examined in a covariate analysis. As an example for serum ferritin, the following SAS code of MIXED procedure will be used to produce the differences in Least Squares (LS) Mean of change in serum ferritin at Months 1, 2, 3, 4, 5, 6, 7, 8, 9, 10, 11, and 12 between deferiprone and placebo groups and the corresponding 95% confidence intervals.

```

proc mixed data=sf;
  class patient base_sf treat month;
  model sf_change = base_sf treat month treat*month /
    noint solution ddfm=kr;
  repeated month / Patient=patient(treat) type=ar(1);
  lsmeans treat*month;
  estimate 'Deferiprone - Placebo at Month 1'
    treat 1 -1
    treat*month  1 0 0 0 0 0 0 0 0 0 0 0
                 -1 0 0 0 0 0 0 0 0 0 0 0 / cl alpha=0.05;
  estimate 'Deferiprone - Placebo at Month 2'
    treat 1 -1
    treat*month  0 1 0 0 0 0 0 0 0 0 0 0
                 0 -1 0 0 0 0 0 0 0 0 0 0 / cl alpha=0.05;
  estimate 'Deferiprone - Placebo at Month 3'
    treat 1 -1
    treat*month  0 0 1 0 0 0 0 0 0 0 0 0
                 0 0 -1 0 0 0 0 0 0 0 0 0 / cl alpha=0.05;
  estimate 'Deferiprone - Placebo at Month 4'
    treat 1 -1
    treat*month  0 0 0 1 0 0 0 0 0 0 0 0
                 0 0 0 -1 0 0 0 0 0 0 0 0 / cl alpha=0.05;
  estimate 'Deferiprone - Placebo at Month 5'
    treat 1 -1
    treat*month  0 0 0 0 1 0 0 0 0 0 0 0
                 0 0 0 0 -1 0 0 0 0 0 0 0 / cl alpha=0.05;
  estimate 'Deferiprone - Placebo at Month 6'
    treat 1 -1
    treat*month  0 0 0 0 0 1 0 0 0 0 0 0
                 0 0 0 0 0 -1 0 0 0 0 0 0 / cl alpha=0.05;

```

```

estimate 'Deferiprone - Placebo at Month 7'
  treat 1 -1
  treat*month  0 0 0 0 0 0  1 0 0 0 0 0
                0 0 0 0 0 0 -1 0 0 0 0 0/ cl alpha=0.05;
estimate 'Deferiprone - Placebo at Month 8'
  treat 1 -1
  treat*month  0 0 0 0 0 0  1 0 0 0 0
                0 0 0 0 0 0 0 -1 0 0 0 0/ cl alpha=0.05;
estimate 'Deferiprone - Placebo at Month 9'
  treat 1 -1
  treat*month  0 0 0 0 0 0 0 0  1 0 0 0
                0 0 0 0 0 0 0 0 -1 0 0 0/ cl alpha=0.05;

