estimate 'Deferiprone - Placebo at Month 10'
  treat 1 -1
  treat*month  0 0 0 0 0 0 0 0 0  1 0 0
                0 0 0 0 0 0 0 0 0 -1 0 0/ cl alpha=0.05;
estimate 'Deferiprone - Placebo at Month 11'
  treat 1 -1
  treat*month  0 0 0 0 0 0 0 0 0  1 0
                0 0 0 0 0 0 0 0 0 0 -1 0/ cl alpha=0.05;
estimate 'Deferiprone - Placebo at Month 12'
  treat 1 -1
  treat*month  0 0 0 0 0 0 0 0 0  1
                0 0 0 0 0 0 0 0 0 0 -1/ cl alpha=0.05;
run;

```

A Kaplan-Meier survival curve for the time to reach a serum ferritin level  $\geq 1000 \mu\text{g/L}$ , an LPI value  $\geq 0.6 \mu\text{M}$ , or a TSAT value  $\geq 60\%$  will be generated for the two treatment groups. Log-rank test will be used for comparing the two survival curves for each of the 3 efficacy endpoints.

As an example, for serum ferritin, the following SAS code of LIFETEST procedure will be used to compare the two survival curves. A variable status is the censoring indicator. A status of 1 indicates an event time when a serum ferritin level reaches  $\geq 1000 \mu\text{g/L}$  and a status of 0 indicates the event of serum ferritin level  $\geq 1000 \mu\text{g/L}$  has not occurred by the end of the study.

```

proc lifetest data=sf method=km plot=(s) graphics;
  time month*status(0);
  strata treat;
run;

```

Trend analysis over time for LPI, TSAT, and SF measures will be performed to compare the rate of change per month in these measures between the two treatment groups. As an example, for serum ferritin, the following SAS code of MIXED procedure will be used to compare the two slopes between the two treatment groups:

```
proc mixed data=sf;
  class treat patient;
  model sf = treat month treat*month / noint solution;
  repeated / type=ar(1) Patient=patient(treat);
  estimate 'Slope for deferiprone' month 1 treat*month 1 0;
  estimate 'Slope for placebo' month 1 treat*month 0 1;
  estimate 'Slope for deferiprone minus placebo' treat*month 1 -1;
run;
```

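### Secondary efficacy tests are all judged at full two-sided 0.05 with no order, adjustment or exploratory label, so their joint error rate is uncontrolled

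*SAP*

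**What the plan says.** SAP 5.2.1 and Protocol 9.1.1 name one primary endpoint, the percentage of patients with SF still below 1000 µg/L at Month 12. SAP 5.1.1 makes ITT the primary population.

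SAP section 5 then sets one decision rule for the whole plan: "A two-sided p-value of 0.05 will be used as the significance level for the determination of statistical significance in all statistical tests".

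SAP 5.2.2 opens its list with "The secondary efficacy endpoints are" and gives six items in no stated order: for each of SF, LPI and TSAT, the percentage still below threshold at each visit and the time to reach the threshold. SAP 5.6 says that the percentages "will be compared between the two treatment groups at each monthly time point as well as at the end of study" by Fisher's exact test, and that the "Log-rank test will be used for comparing the two survival curves for each of the 3 efficacy endpoints". It adds a between-arm slope comparison for each measure, and the shells give this a p-value column. It also plans monthly LS-mean differences with 95% CIs; those shells have a CI column and no p-value column.

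The shells add by-visit t-tests on values and changes. SAP 5.1.2 repeats the efficacy endpoints in the PP population, whereas Protocol 9.3.2 planned only the primary endpoint there. SAP section 1 gives the SAP precedence over the protocol on planned analyses.

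**The concern.** The SAP is not merely silent on multiplicity. It gives a positive rule under which any efficacy p-value at or below 0.05 counts as statistically significant. No secondary test is conditional on the primary, and no list says which secondaries matter most. In Table 14.2.1.5 the primary result is one row of 13, under the same p-value column as every other visit.

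Two situations are at stake. If the primary fails, the plan as written still allows a significant result to be reported for LPI, for TSAT or at some single visit. If the primary succeeds, LPI and TSAT results can still be picked from 12 visits and several methods without error control. The second matters more here, because the trial is powered to make a primary failure unlikely.

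**Working it through.** **The plan's own figure.** Protocol 9.2: "The sample size for this study is 64 patients, randomized in a 1:1 ratio to the two arms". It continues: "With this number of patients, there will be over 90% power to detect a statistically significant difference" at alpha 0.05, "if the deferiprone arm and the placebo arm have an expected incidence of 70% and 20%, respectively". With 32 per arm the pooled rate is (0.70 + 0.20)/2 = 0.45.
- SE under the null: √(2 × 0.45 × 0.55/32) = 0.1244.
- SE under the alternative: √((0.70 × 0.30 + 0.20 × 0.80)/32) = 0.1075.
- Power: Φ((0.50 − 1.96 × 0.1244)/0.1075) = Φ(2.38) = 99.1%.
- Exact enumeration of the planned Fisher test: 98.3%.

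The statement of over 90% holds as a lower bound.

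**Counting the tests (SAP 5.2.2, 5.6 and shells).**
- Fisher: 3 measures × 12 post-baseline months = 36; less the primary = 35.
- Log-rank: 3. Named secondary tests: 35 + 3 = 38.
- Slopes: 3, giving 38 + 3 = 41.
- Not counted: by-visit t-tests, (13 + 12) rows × 3 measures = 75; 3 baseline Fisher rows; PP repeats; and 36 LS-mean contrasts (12 × 3), which are planned as CIs.

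**Joint error with one test per endpoint.** For m independent tests, the chance of at least one false positive is 1 − 0.95^m. For m normal test statistics with common correlation ρ it is

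1 − ∫ φ(u) [Φ((1.96 − √ρ·u)/√(1−ρ)) − Φ((−1.96 − √ρ·u)/√(1−ρ))]^m du.

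| Family | ρ = 0 | 0.5 | 0.7 | 0.9 |
|---|---|---|---|---|
| 2 log-rank tests (LPI, TSAT) | 9.75% | 9.1% | 8.4% | 7.0% |
| 3 log-rank tests | 14.3% | 12.5% | 10.9% | 8.4% |
| 6 endpoints, one test each | 26.5% | 20.7% | 16.4% | 10.8% |

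The documents give no correlations, so the whole range is shown. The first row applies when SF truly responds but LPI and TSAT do not. The six-endpoint row counts each visit-wise endpoint once although it is tested at 12 visits.

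**Joint error for the 38 named tests.** Independence would give 1 − 0.95^38 = 85.8%. That is too high, because visits and measures are correlated and Fisher's test is conservative: its exact size at 32 per arm is 2.4% at a common rate of 20%, 3.2% at 45% and 1.1% at 90%. Two simulations with no treatment effect and complete follow-up allow for both.
- *Linear growth:* baseline 400 (SD 100), slope 45 per month (SD 20), AR(1) residual SD 60 with correlation 0.5, threshold 1000, the same scale for all three measures, 1,500 trials per setting. With between-measure correlation 0.3, 0.5 and 0.8: 23.5%, 23.1% and 20.1%.
- *Varied scenarios:* between-measure correlation 0, 0.5 or 0.8; low or high visit noise; 20% or 45% not reaching the threshold by Month 12; cumulative or visit-specific status; 2,500 trials per scenario. Result: 24% to 62%, exceeding 50% only with noisy, visit-specific status.

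The three log-rank tests alone gave 12-14% and 11-17% in the two simulations, close to the table.

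**Effect of gating.** In a fixed sequence starting with the primary, each step is tested at 0.05 only if every earlier step was significant, so familywise error is at most 5%. With no effect at all, any confirmatory claim first needs a significant primary, which by the Fisher size above happens in about 2.4-3.2% of trials at common rates of 20-45%.

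**The case against.** The strongest reply is that the confirmatory question is already protected: one primary endpoint, one primary population, no interim analysis, a Phase 4 trial, and no statement that a secondary result would support a claim if the primary failed. At the planned 70% v 20% the primary fails in only about 1.7% of trials (100 − 98.3), so a failed primary followed by a secondary claim should be rare. Whether secondaries need formal control when no claim is announced is partly convention. All of this stands. It limits the weight of the point but does not remove it: the SAP does not call the secondaries supportive, its rule treats them as significance tests, and a true SF effect does not protect LPI and TSAT.

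Three stronger readings are tempting and should be resisted.
- A reader might infer that a false secondary claim is likely. For the 38 tests most scenarios fall well below one half, and every figure for that family assumes no effect on anything, which the plan does not expect.
- A reader might add the 36 LS-mean contrasts to the count. A CI excluding zero is equivalent to a test at 0.05, but the plan shows these as CIs and schedules no significance judgement for them.
- Protocol 1.3 says "The objectives are to determine whether such a regimen can postpone saturation of transferrin and thus the appearance of labile plasma iron", which seems to make TSAT and LPI the trial's objectives. That is the Rationale section. The formal objectives (Protocol 2.1 and 2.2, SAP 2.1 and 2.2) are lessening progressive iron overload, and safety; Protocol 2.1 refers the primary objective to the single SF endpoint.

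The simulations also ignore the mandatory withdrawal after two consecutive SF values ≥1000 µg/L, which would thin the later visits.

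**Conclusion.** The point holds as a lack of error control across the secondary efficacy tests; the primary comparison, its alpha and its power are untouched. With no treatment effect, the joint error is about 8-14% for the three log-rank tests and 11-26% for six endpoints at one test each, against a nominal 5%. These two ranges depend only on an assumed common correlation between 0.9 and 0. The 20-62% for the 38 named tests is softer, since it depends on variances, correlations and trajectories that the documents do not supply; its direction is firm, its size is not. In the more realistic case of a true SF effect with no LPI or TSAT effect, the excess is modest for the two log-rank tests (about 7-10%), before their 24 visit-wise Fisher tests (2 × 12) are counted. The supportable description is uncontrolled and above 5%. This is a cheap improvement to the plan and does not threaten its main conclusion.

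**What to change.** Replace the general sentence in SAP section 5 with a rule to this effect:
- The confirmatory test is the Month 12 comparison of SF <1000 µg/L in the ITT population, at two-sided 0.05.
- If it is significant, a short list of key secondaries is tested in a fixed order, each at two-sided 0.05, stopping at the first non-significant result. The three time-to-threshold log-rank tests are a natural list. The sponsor chooses the order and fixes it before unblinding.
- The visit-wise percentages remain secondary endpoints. They and the slopes, LS-mean differences, by-visit t-tests and PP repeats are reported with estimates, 95% CIs and nominal p-values, with no claim of significance.
- The affected table shells carry a matching footnote.

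An even split across the six endpoints would also control error, but at 0.05/6 = 0.0083 per test; Fisher power for a 70% v 20% difference would then fall from 98.3% to 90.4%, and each visit-wise endpoint would need one pre-specified time point or a summary test. The fixed sequence avoids that loss.

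The cost is SAP wording and footnotes: no extra patients, data or analyses. The downside is that a nominally significant result outside the sequence, or below a failed step, cannot be claimed as confirmatory.

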### **5.1 Study Populations**

#### **5.1.1 Intent-to-Treat Population**

The intent-to-treat (ITT) population will be composed of patients who were randomized, have received at least one dose of study medication, and have had at least one post-baseline measurement on the efficacy variables. All efficacy endpoints will be analyzed for the ITT population, which represents the primary analysis population.

#### **5.1.2 Per Protocol Population**

The per protocol (PP) population will represent the secondary analysis population, and will be composed of the same patients as in the intent-to-treat (ITT) population without major protocol deviations. Patients with major protocol deviation(s) will be determined before the database is locked. The efficacy endpoints will be analyzed for this population as well.

#### **5.1.3 Safety Population**

The safety population will be composed of patients who have received at least one dose of study medication.

## **5.2 Efficacy Endpoints**

#### **5.2.1 Primary Efficacy Endpoint**

The primary efficacy endpoint is the percentage of patients who still have a serum ferritin level < 1000 µg/L at Month 12.

### **5.2.2 Secondary Efficacy Endpoints**

The secondary efficacy endpoints are:

- The percentage of patients whose serum ferritin level is still less than 1000  $\mu\text{g}/\text{L}$  at each visit
- The percentage of patients whose LPI value is still less than 0.6  $\mu\text{M}$  at each visit
- The percentage of patients whose TSAT value is still less than 60% at each visit
- Time to reach a serum ferritin level  $\geq 1000 \mu\text{g}/\text{L}$  (Note: a patient is to be withdrawn from the study only if the repeated serum ferritin level is  $\geq 1000 \mu\text{g}/\text{L}$ .)
- Time to reach an LPI value  $\geq 0.6 \mu\text{M}$
- Time to reach a TSAT value  $\geq 60\%$

### **5.3 Safety Endpoints**

The safety endpoints are:

- Adverse events (AEs): Frequency, intensity, time to onset, duration, and relatedness to study drug
- Serious adverse events (SAEs): Frequency, intensity, time to onset, duration, and relatedness to study drug
- Number of discontinuations due to AEs
- Growth parameters: Weight, height, and height velocity, as classified using the Z-score system
- Change in prolactin level from baseline to Month 12

### **5.4 Patient Disposition and Drug Exposure**

The numbers of patients who were screened, randomized, exposed to the study medication, who completed the study, and who withdrew from the study (along with reasons for withdrawals) will be presented.

### **5.5 Patient Characteristics**

Patient characteristics at baseline, including demographics, will be summarized with descriptive statistics for continuous variables and with frequency tables for categorical variables. Medical history will be summarized using the Medical Dictionary for Regulatory Activities (MedDRA) version 23.0 or higher.

## 5.6 Analysis of Efficacy

The percentage of patients who have not reached levels of  $LPI \geq 0.6 \mu M$ ,  $TSAT \geq 60\%$ , or  $SF \geq 1000 \mu g/L$  will be compared between the two treatment groups at each monthly time point as well as at the end of study, using the Fisher's exact test. (Note: the repeated SF value will be used to determine this for those patients whose SF is  $\geq 1000 \mu g/L$ .)

The effect of baseline value on each of the 3 efficacy endpoints will be examined in a covariate analysis. As an example for serum ferritin, the following SAS code of MIXED procedure will be used to produce the differences in Least Squares (LS) Mean of change in serum ferritin at Months 1, 2, 3, 4, 5, 6, 7, 8, 9, 10, 11, and 12 between deferiprone and placebo groups and the corresponding 95% confidence intervals.

```

proc mixed data=sf;
  class patient base_sf treat month;
  model sf_change = base_sf treat month treat*month /
    noint solution ddfm=kr;
  repeated month / Patient=patient(treat) type=ar(1);
  lsmeans treat*month;
  estimate 'Deferiprone - Placebo at Month 1'
    treat 1 -1
    treat*month  1 0 0 0 0 0 0 0 0 0 0 0
                 -1 0 0 0 0 0 0 0 0 0 0 0 / cl alpha=0.05;
  estimate 'Deferiprone - Placebo at Month 2'
    treat 1 -1
    treat*month  0 1 0 0 0 0 0 0 0 0 0 0
                 0 -1 0 0 0 0 0 0 0 0 0 0 / cl alpha=0.05;
  estimate 'Deferiprone - Placebo at Month 3'
    treat 1 -1
    treat*month  0 0 1 0 0 0 0 0 0 0 0 0
                 0 0 -1 0 0 0 0 0 0 0 0 0 / cl alpha=0.05;
  estimate 'Deferiprone - Placebo at Month 4'
    treat 1 -1
    treat*month  0 0 0 1 0 0 0 0 0 0 0 0
                 0 0 0 -1 0 0 0 0 0 0 0 0 / cl alpha=0.05;
  estimate 'Deferiprone - Placebo at Month 5'
    treat 1 -1
    treat*month  0 0 0 0 1 0 0 0 0 0 0 0
                 0 0 0 0 -1 0 0 0 0 0 0 0 / cl alpha=0.05;
  estimate 'Deferiprone - Placebo at Month 6'
    treat 1 -1
    treat*month  0 0 0 0 0 1 0 0 0 0 0 0
                 0 0 0 0 0 -1 0 0 0 0 0 0 / cl alpha=0.05;

```

```

estimate 'Deferiprone - Placebo at Month 7'
  treat 1 -1
  treat*month  0 0 0 0 0 0  1 0 0 0 0 0
                0 0 0 0 0 0 -1 0 0 0 0 0/ cl alpha=0.05;
estimate 'Deferiprone - Placebo at Month 8'
  treat 1 -1
  treat*month  0 0 0 0 0 0  1 0 0 0 0
                0 0 0 0 0 0 0 -1 0 0 0 0/ cl alpha=0.05;
estimate 'Deferiprone - Placebo at Month 9'
  treat 1 -1
  treat*month  0 0 0 0 0 0 0 0  1 0 0 0
                0 0 0 0 0 0 0 0 -1 0 0 0/ cl alpha=0.05;
estimate 'Deferiprone - Placebo at Month 10'
  treat 1 -1
  treat*month  0 0 0 0 0 0 0 0 0  1 0 0
                0 0 0 0 0 0 0 0 0 -1 0 0/ cl alpha=0.05;
estimate 'Deferiprone - Placebo at Month 11'
  treat 1 -1
  treat*month  0 0 0 0 0 0 0 0 0  1 0
                0 0 0 0 0 0 0 0 0 0 -1 0/ cl alpha=0.05;
estimate 'Deferiprone - Placebo at Month 12'
  treat 1 -1
  treat*month  0 0 0 0 0 0 0 0 0  1
                0 0 0 0 0 0 0 0 0 0 -1/ cl alpha=0.05;
run;

```

A Kaplan-Meier survival curve for the time to reach a serum ferritin level  $\geq 1000 \mu\text{g/L}$ , an LPI value  $\geq 0.6 \mu\text{M}$ , or a TSAT value  $\geq 60\%$  will be generated for the two treatment groups. Log-rank test will be used for comparing the two survival curves for each of the 3 efficacy endpoints.

As an example, for serum ferritin, the following SAS code of LIFETEST procedure will be used to compare the two survival curves. A variable status is the censoring indicator. A status of 1 indicates an event time when a serum ferritin level reaches  $\geq 1000 \mu\text{g/L}$  and a status of 0 indicates the event of serum ferritin level  $\geq 1000 \mu\text{g/L}$  has not occurred by the end of the study.

```

proc lifetest data=sf method=km plot=(s) graphics;
  time month*status(0);
  strata treat;
run;

```

Trend analysis over time for LPI, TSAT, and SF measures will be performed to compare the rate of change per month in these measures between the two treatment groups. As an example, for serum ferritin, the following SAS code of MIXED procedure will be used to compare the two slopes between the two treatment groups:

```
proc mixed data=sf;
  class treat patient;
  model sf = treat month treat*month / noint solution;
  repeated / type=ar(1) Patient=patient(treat);
  estimate 'Slope for deferiprone' month 1 treat*month 1 0;
  estimate 'Slope for placebo' month 1 treat*month 0 1;
  estimate 'Slope for deferiprone minus placebo' treat*month 1 -1;
run;
```

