## 5.7 Analysis of Safety

Descriptive statistics (mean, standard deviation, minimum, and maximum) will be produced for continuous variables, and frequency tables will be produced for discrete variables by treatment group. Summaries of adverse events and serious adverse events will be produced by treatment group. Shift tables will be generated for comparing the screening/baseline values and end of study values of the relevant measures.

The following safety data will be summarized by treatment group:

- Adverse events (AEs), adverse drug reactions (ADRs), serious adverse events (SAEs), and serious adverse drug reactions (SADRs)
- Number of discontinuations due to AEs
- Hematology assessments
- Biochemistry assessments
- Urinalysis
- Vital signs
- Prior and concomitant medications

Prolactin is measured at baseline and Month 12. The change in prolactin level from baseline to Month 12 will be compared between the two treatment groups using an ANCOVA model with baseline value as a covariate and treatment as the main factor.

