#### **14.2 Efficacy analyses**

##### **14.2.1 Serum ferritin ( $\mu\text{g}/\text{L}$ )**

Table 14.2.1.1 Serum ferritin ( $\mu\text{g}/\text{L}$ ) at each assessment – ITT population

Table 14.2.1.1a Serum ferritin ( $\mu\text{g}/\text{L}$ ) at each assessment – PP population

Table 14.2.1.2 Change in serum ferritin ( $\mu\text{g}/\text{L}$ ) from baseline at each follow-up assessment – ITT population

Table 14.2.1.2a Change in serum ferritin ( $\mu\text{g}/\text{L}$ ) from baseline at each follow-up assessment – PP population

Table 14.2.1.3 LS Means for change in serum ferritin ( $\mu\text{g}/\text{L}$ ) from ANCOVA model at each follow-up assessment – ITT population

Table 14.2.1.3a LS Means for change in serum ferritin ( $\mu\text{g}/\text{L}$ ) from ANCOVA model at each follow-up assessment – PP population

Table 14.2.1.4 Trend analysis for serum ferritin ( $\mu\text{g}/\text{L}$ ) over time – ITT population

Table 14.2.1.4a Trend analysis for serum ferritin ( $\mu\text{g}/\text{L}$ ) over time – PP population

Table 14.2.1.5 Percent of patients who had serum ferritin  $< 1000 \mu\text{g}/\text{L}$  at each assessment – ITT population

Table 14.2.1.5a Percent of patients who had serum ferritin  $< 1000 \mu\text{g}/\text{L}$  at each assessment – PP population

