16.2.9.7 Listing of transfusion

16.2.9.8 Listing of exposure

16.2.9.9 Listing of concomitant medications

**TABLE SHELLS**

The following table shells provide a framework for the display of data from this study. These tables may not be designed exactly as shown in the shells, but are intended to reflect the general layout of the data that will be included in the clinical study report.

Note that 'c' in the table shells indicates an alphanumeric character and 'x' indicates a number from 0 to 9.

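### SAP 5.6 code enters continuous baseline ferritin as a factor, leaving the baseline-adjusted monthly differences imprecise, with intervals that can be unreliable, or not estimable

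*SAP*

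**What the plan says.** SAP 5.6 states the purpose: "The effect of baseline value on each of the 3 efficacy endpoints will be examined in a covariate analysis". It then says that the printed PROC MIXED code, given as the ferritin example, will be used to produce the treatment differences in change at Months 1 to 12 with 95% confidence intervals. The code declares "class patient base_sf treat month" and fits "model sf_change = base_sf treat month treat*month", with AR(1) correlation within patient and Kenward-Roger degrees of freedom.

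The results go to Table 14.2.1.3 and its per-protocol counterpart, whose titles describe LS means "from ANCOVA model at each follow-up assessment". The shell shows LS means, differences and 95% intervals, without p-values. In SAP 5.7, the prolactin analysis is described as "using an ANCOVA model with baseline value as a covariate and treatment as the main factor". Nothing in either document divides baseline ferritin into categories. The slope model later in 5.6 declares only "class treat patient" and leaves `month` out, so the SAP does use the continuous form when it wants a slope.

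**The concern.** A variable in CLASS gets one parameter per distinct value. Baseline ferritin is nearly unique to each child, so the model spends more than 50 parameters on it where one slope was intended. Three things follow.

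- The stated question, how baseline affects the endpoint, is not answered. The output lists level effects and no slope.
- The arms can be compared in level only through children whose baseline value also occurs in the other arm. If there are none, all 12 differences are non-estimable.
- Near patient-specific levels absorb stable differences between children. The fitted AR(1) correlation can then fall, and the reported standard error need not show the precision that was lost.

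Table 14.2.1.3 and its per-protocol version are the only planned baseline-adjusted ferritin results. Tables 14.2.2.3 (LPI) and 14.2.3.3 (TSAT) are affected only if the template is copied unchanged.

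**Working it through.** **The plan's own figure.** The documents give no precision for this model. Their only power figure is over 90% for the primary comparison (Protocol 9.2). Exact Fisher enumeration at 32 per arm, 70% versus 20%, gives 98.3%. That claim stands and is not touched here.

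**Inputs.** From the documents: 32 children per arm (SAP 3.2); screening ferritin above 200 and up to 600 µg/L (Protocol 4.2); 12 monthly visits; AR(1). Assumed: Day 0 ferritin in 201–600, either uniform or normal with mean 400 and SD 80 or 50; and the true covariance. The shells show ferritin as whole numbers, but that is display only: "These tables may not be designed exactly as shown in the shells". Recording to one decimal was therefore tried as well.

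**Identification.** For baseline level b, arm d and month k, the fitted mean is β_b + τ_d + μ_k + γ_dk. The contrast at month k is τ_1 − τ_2 + γ_1k − γ_2k. If no level occurs in both arms, adding c to every β_b in the deferiprone arm and subtracting c from τ_1 leaves all fitted means unchanged while the contrast moves by c. It is therefore not estimable. One shared level removes this freedom. In simulated data sets the contrasts were estimable exactly when at least one value was shared.

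**How many values are shared** (uniform, 400 whole numbers):

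- Distinct levels: 400 × (1 − 0.9975^64) = 59.2.
- Values in both arms: 400 × (1 − 0.9975^32)² = 2.4.
- Chance of none, approximately: (0.9975^32)^32 = 0.077.

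Simulation (20,000 draws), uniform / SD 80 / SD 50:

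- Distinct levels: 59.2 / 57.3 / 54.0.
- Shared values: 2.4 / 3.3 / 4.7, held by 4.9 / 6.9 / 10.4 children.
- Chance of none: 0.076 / 0.028 / 0.004, and 0.102 for uniform 201–650.
- Chance of none with one decimal: 0.776 (uniform) and 0.563 (SD 50).

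**Precision and coverage where estimable.** Both versions were fitted by REML with AR(1) and Kenward-Roger, using 800 estimable draws per setting and the full 12-entry Month 12 contrast. Ratios are CLASS to linear covariate. Entries are uniform / SD 80 / SD 50, without withdrawal.

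| True covariance | Error (RMSE) ratio | Median CI-width ratio | CI misses, CLASS (%) |
|---|---|---|---|
| AR(1) 0.8 | 2.78 / 2.50 / 1.98 | 2.61 / 2.25 / 1.90 | 4.4 / 5.6 / 6.0 |
| Random intercept 0.5 + AR(1) 0.5 | 3.05 / 2.78 / 2.35 | 1.49 / 1.34 / 1.25 | 32.3 / 27.5 / 25.0 |
| Random intercept, ICC 0.5 | 3.16 / 2.59 / 2.17 | 1.08 / 1.03 / 0.98 | 45.8 / 37.5 / 35.9 |
| Random intercept, ICC 0.8 | 3.82 / 3.21 / 2.70 | 0.82 / 0.84 / 0.87 | 64.2 / 55.2 / 44.8 |

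The linear covariate missed 3.0–5.6% throughout. The fitted correlation shows why: at ICC 0.8 it was 0.20–0.44 with CLASS against 0.80 with the linear covariate, while under true AR(1) 0.8 both gave 0.80.

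**With withdrawal.** Assumed: 30% of deferiprone and 80% of placebo children leave, mirroring the 70%/20% planning rates, at random, with last visit uniform over Months 6–11.

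- Month 12 error ratio: 1.43–2.60.
- Width ratio: 1.51–1.94 under AR(1), 0.80–1.24 under the other structures.
- Misses with CLASS: 4.1–5.0% under AR(1), 16.4–47.7% otherwise. Linear: 2.9–5.5%.

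A separate calculation with correlations of 0.5–0.9, uniform baselines and withdrawal at the same rates, with departures spread over an earlier range of visits, gave median standard-error ratios of 2.1–2.9 at Month 1 and 1.5–2.2 at Month 12. Early visits are thus hit harder than Month 12.

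**LPI and TSAT, if the template is copied** (assumed ranges LPI 0–0.6 µM, TSAT 20–100%). Non-estimability is negligible for two-decimal LPI and whole-number TSAT, and 28% for one-decimal TSAT. The SAP shells show TSAT both ways.

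**The case against.** The SAP's prose states the right intent, and the code is offered as an example. It cannot run as printed, because the REPEATED statement begins "repeated month / Patient=patient(treat) type=ar(1" where PROC MIXED expects `subject=`. A programmer must therefore edit it with the prose in view. The `solution` option would also print 50-odd ferritin coefficients, which is hard to overlook. The intervals are valid under the AR(1) structure the SAP specifies; poor coverage needs a patient-level component whose size is assumed. The complete-data ratios ignore the withdrawal built into the design, and high non-estimability needs one-decimal recording, which no passage supports. Finally, change in ferritin is neither the primary nor a listed secondary endpoint, the table carries no p-value, and unadjusted changes are tabulated separately.

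Much of this stands as a limit on size and reach. The Month 12 figures with withdrawal are the more realistic ones, although the simulated withdrawal was random whereas the protocol triggers it by ferritin itself. It does not remove the error. The SAP commits to the code for ferritin, and a continuous variable in CLASS is valid syntax. Once the REPEATED option is corrected, the step returns numbers without an error whenever one value is shared. In every setting tried, the CLASS version was less accurate than the linear one.

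**Conclusion.** The concern holds. The code contradicts the SAP's own description of the analysis, and following it gives a worse result or none. That the specification is wrong rests on the text alone; the sizes rest on the assumed baseline spread, recording precision, covariance and withdrawal pattern.

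The correction should be made, but the reach is limited. It covers the baseline-adjusted ferritin tables, and those for LPI and TSAT only if the code is reused. The primary Fisher test, the listed secondary endpoints, and the Kaplan-Meier and trend analyses do not depend on this model.

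**What to change.** Change the CLASS statement to `class patient treat month;` and leave `base_sf` in MODEL as a continuous covariate. State in SAP 5.6 that baseline LPI and TSAT enter their models in the same way. In the same edit, replace `Patient=` with `subject=` in both REPEATED statements of that section.

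The cost is one word deleted, one option name corrected in two places and one sentence added. No data collection or design element changes.
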